11.3.1. Investigator Information

Site-specific contact information may be provided in a separate document.

11.3.2. Protocol Signatures

The sponsor's responsible medical officer will approve the protocol, confirming that, to the best of his or her knowledge, the protocol accurately describes the planned design and conduct of the study.

After reading the protocol, each principal investigator will sign the protocol signature page and send a copy of the signed page to a Lilly representative.

Attachment 1. Protocol CXAD Study Schedule

Baseline, During and Poststudy Assessments

Relative Day Within a Cycle	Baseline		Cycle 1		Cycle 2	Cycle 3-n	Follow-Up			LT FU ^a	Comments
	<28 days	<7 days	1	15	1	1	30 day	60 day	90 day		
Visits							801	802	803	804	
Informed Consent	x										Informed Consent Form signed (prior to performance of any protocol-specific tests/procedures).
Medical History	x										Including alcohol/tobacco use and other relevant habits assessments.
Physical Examination/ Vital Signs	x		x		x		x				Full examination at baseline. Focused examination at other time points. During the study treatment period, occurs within 3 days prior to first day of each cycle. Includes recent height (baseline only), weight, and vital signs (blood pressure, pulse, temperature, and respiratory rate [at baseline and as indicated in Section 7.2.1.2]). See Section 7.2.1.2 for a detailed description of vital sign collection on study.
ECHO	x										Local. ECHOs may be performed on study as clinically indicated to determine LVEF/LV dysfunction and any change in cardiac size or function.

Relative Day Within a Cycle	Baseline		Cycle 1		Cycle 2	Cycle 3-n	Follow-Up				Comments
	<28 days	<7 days	1	15	1	1	30 day	60 day	90 day	LT FU ^a	
Visits							801	802	803	804	
ECG		x	x	x	x						
Obtain ECGs before any associated blood draws.
 
At baseline, triplicate ECG will be obtained, on which QTcF must be <450 ms (calculated from one ECG using Fridericia’s Correction Formula and confirmed with 2 additional ECGs).
 
Cycle 1 Day 1: ECG will be conducted 30 mins post LY2510924 dose.
 
Cycle 1 Day 15 and Cycle 2 Day 1: ECGs will be conducted predose.
 
All ECGs will be done in triplicate.

Concomitant Meds	x		x		x	x	x	x	x		Throughout study as needed.
ECOG Performance Status	x		x		x	x	x	x	x		
HIV, Hepatitis B, and Hepatitis C Testing	x										All tests completed locally. Hepatitis B (HBsAg, Anti-HBc) Hepatitis C (Anti-HCV, HCV RNA)
Hematology		x	x	x	x	x	x	x	x		Local. Complete blood count with differential. If any abnormalities, will follow beyond the 30-day FUP, as clinically indicated

Relative Day Within a Cycle	Baseline		Cycle 1		Cycle 2	Cycle 3-n	Follow-Up				Comments
	<28 days	<7 days	1	15	1	1	30 day	60 day	90 day	LT FU ^a	
Visits							801	802	803	804	
Serum Chemistry and Liver Function Testing		x	x	x	x	x	x	x	x		Local and central. See Attachment 2 . If any abnormalities, will follow beyond the 30-day FUP, as clinically indicated. To include liver enzyme panel.
Tumor Markers in Blood	x		x		x	x	x	x	x		Local. If applicable to tumor type of the patient (eg, CEA in patients with colorectal cancer or CA125 in patients with ovarian cancer). Obtain predose, if dose administered.
Coagulation		x									Local. Includes prothrombin time, aPTT and INR. As clinically indicated on study and prior to any procedures (eg, tumor biopsy).
Thyroid Function Tests		x	x		x	x	x	x	x		Local. Includes TSH and ft4. Additionally, measure if there is clinical suspicion of an adverse event related to the endocrine system.
Urinalysis		x	x		x	x	x	x	x		Local. See Attachment 2 . If any abnormalities, will follow beyond the 90-day FUP, as clinically indicated.
CTCAE v 4.03 Grading		x	x	x	x	x	x	x	x	x	To be reported only after study eligibility is confirmed. Throughout study as needed. Refer to Section 8.1.2.6 for reporting guidelines. Data on SAEs that occur before the end of trial will be stored in the collection database and the Lilly Safety System.
Urine or Serum Pregnancy Test		x									Local. As clinically indicated while on study.

	Baseline		Cycle 1		Cycle 2	Cycle 3-n	Follow-Up				Comments
	<28 days	<7 days	1	15	1	1	30 day	60 day	90 day	LT FU ^a	
Relative Day Within a Cycle	<28 days	<7 days	1	15	1	1	30 day	60 day	90 day	LT FU ^a	Assessments to be performed at the times stipulated in the table and as clinically required in the management of the patient. All assessments to be performed pre-infusion unless stated otherwise.
Visits							801	802	803	804	
Tumor Tissue		≤3 yrs prior			D7						Central. Core or excisional biopsy of a tumor lesion or a recent biopsy defined by ≤3 years since last documented progression of disease. Patients for whom newly obtained samples cannot be obtained such as in cases of inaccessibility or patient safety concern, an archived specimen can be submitted upon agreement from sponsor. If a fresh biopsy is obtained, an archival specimen (if available) should also be submitted for comparison. On-treatment sample (Cycle 2 Day 7 ±7 days): mandatory for ovarian expansion arm (Phase 1b), optional in Phase 1a and pancreatic expansion arm in Phase 1b.
PK Sampling			D1 & 2	D15 & 16	x	C3, C4, & C6			x		See PK Sampling Attachment 4 for exact timing.
Serum, Plasma, and Whole Blood Samples for Biomarkers		x	See Attachment 4 for exact timing.				x				Baseline sample for whole blood only, and must be collected ≤7 days prior to Cycle 1 Day 1. See Attachment 4 for exact timing.
Radiological Tumor Assessment	x				x		x				Local. CT scans will begin within 7 days prior to starting Cycle 3 and every other cycle afterwards including follow-up (approximately 8 weeks apart).

Relative Day Within a Cycle	Baseline		Cycle 1		Cycle 2	Cycle 3-n	Follow-Up				Comments
	<28 days	<7 days	1	15	1	1	30 day	60 day	90 day	LT FU ^a	
Visits							801	802	803	804	
Blood for pharmacogenetics		x									It is highly recommended to draw the whole blood sample on Cycle 1 Day 1 prior to the first dose; however, it can be collected later during the study if necessary.
Other safety or laboratory assessments; for example, immunogenicity					x	C4			x		Note: Day 1 sample should be taken prior to durvalumab and LY2510924.
Survival/ subsequent anticancer therapy							x	x	x	x	At long-term FUP, at least every 12 weeks ±7days until patient’s death or study completion.
Durvalumab			x		x	x					In clinic on Day 1 of each cycle.
LY2510924			Days 1-28		Days 1-28	Days 1-28					LY2510924 will be self-administered SQ daily. On Cycle 1 Days 1, 2, 15 and 16 and on Cycles 2 to 4 Day 1, LY2510924 should be taken at the clinic (time and date recorded) after a blood sample is taken for LY2510924 PK but prior to the start of durvalumab (refers to Day 1 of each cycle only).
Dispense study drugs and assess compliance			x		x	x					Collect drug diary prior to dispensing study drug for cycle.

Relative Day Within a Cycle	Baseline		Cycle 1		Cycle 2	Cycle 3-n	Follow-Up				Comments
	<28 days	<7 days	1	15	1	1	30 day	60 day	90 day	LT FU ^a	
Visits							801	802	803	804	
Dispense/ collect patient diaries			x		x	x					Patients will complete diaries once per cycle.

Abbreviations: aPTT = activated partial thromboplastin time; C = cycle; CEA = carcinoembryonic antigen; CT = computer tomography; CTCAE = Common Terminology Criteria for Adverse Events; D = day; ECG = electrocardiogram; ECOG = Eastern Cooperative Oncology Group; FUP = follow-up
 HBsAg = hepatitis B surface antigen; HBc = hepatitis B core antibody; HCV = hepatitis C virus; HIV = human immunodeficiency virus; INR = international normalized ratio of prothrombin time; LTFU = long-term follow-up; n = cycle number; LV = left ventricular; LVEF = left ventricular ejection fraction; PK = pharmacokinetic; QTcF = Fridericia’s formula corrected QT interval; RNA = ribonucleic acid; SAE = serious adverse event; SQ = subcutaneous; TSH = thyroid-stimulating hormone; yrs = years.

^a Long-term follow-up begins the day after the 90-day follow-up is completed and continues until the patient’s death or end of trial (approximately every 12 weeks ±7 days the patient will be contacted).

Continued Access and Post Continued Access Assessments

	Cycle n	Follow-Up (days) ^a			Comments
Relative Day Within a Cycle	1	30	60	90	
Visit	501-5XX	901	902	903	
CTCAE v 4.03 grading	x	x	x	x	To be reported only after study eligibility is confirmed. Throughout study as needed. Refer to Section 8.1.2.6 for reporting guidelines. Data on SAEs that occur before the end of trial will be stored in the collection database and the Lilly Safety System.
Durvalumab	x				In clinic on Day 1 of each cycle. Patients will continue to receive study drug(s) at the same dose and schedule as when in the main study.
LY2510924	x				LY2510924 will be self-administered SQ daily.

Abbreviations: CTCAE = Common Terminology Criteria for Adverse Events; n = cycle number; SAE = serious adverse event; SQ = subcutaneous.

^a Continued access follow-up begins 1 day after the patient and the investigator agree that the patient will no longer continue treatment in the continued access period and lasts approximately 90 days. No follow-up procedures will be performed for a patient who withdraws informed consent unless he or she has explicitly provided permission and consent.

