5.2. Rationale for Protocol Amendment (a)

The I2V-MC-CXAD protocol was amended to make the following changes:

- include FOLFOX as an accepted prior therapy for pancreatic cancer
- allow for enrollment of patients with celiac disease if their disease is controlled only with diet
- add echocardiography at baseline to document initial left ventricular (LV) function. Additionally, echocardiography may be performed on-study as clinically indicated to determine left ventricular ejection fraction (LVEF)/LV dysfunction and any change in cardiac size or function. An echocardiography guidance was included as a protocol attachment ([Attachment 12](#)).
- exclude patients with history of QT interval prolongation, history of uncontrolled cardiac arrhythmias or congenital long QT syndrome, or who require drugs known to cause QT prolongation
- change the exclusion criterion for mean QTc interval from ≥ 470 ms to ≥ 450 ms to align with ICH E14 guidelines
- observe the initial patient in the 40-mg cohort in Phase 1a for 2 weeks, after which additional patients will be enrolled after notification from the sponsor. This allows for a

safety assessment prior to enrolling subsequent patients since this dose level has not previously been investigated.

- clarify that final analysis will be conducted no more than 12 months after the last patient enters treatment
- allow dose interruption up to 12 weeks. Management of immune-mediated adverse events (AEs), including steroid tapering, allows a 12-week window for resolution before discontinuing study treatment.
- add dose-limiting toxicity (DLT) and LY2510924 discontinuation criteria of \geq Grade 3 QT prolongation AE per Common Terminology Criteria for Adverse Events (CTCAE) criteria
- clarify an exclusion to the DLT list. Grade 3 thrombocytopenia not associated with bleeding that requires clinically significant medical intervention and improves by at least 1 grade within 3 days is not considered a DLT.
- clarify LY2510924 dose adjustments, delays, and discontinuations and revise a discontinuation criterion from LY2510924 treatment. Patients with combined elevated aspartate aminotransferase (AST)/alanine aminotransferase (ALT) AND total bilirubin values meeting discontinuation parameters as described in the DLT definition should be considered for permanent discontinuation based on clinical judgment.
- include scheduled electrocardiogram (ECG) assessments to assess QT interval length periodically during study therapy

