7.2.1.1. LY2510924

In Phase 1a, LY2510924 will be self-administered SQ at rotated injection sites every day for 28 days as outlined in a dose escalation schema; in Phase 1b, LY2510924 will be self-administered SQ for 28 days at the selected Phase 1a dose.

Approximately 30 minutes prior to dose administration, the vials should be removed from the refrigerated storage area 2°C to 8°C and allowed to equilibrate to ambient room temperature prior to injection. Study drug must be administered within 6 hours after removal from the refrigerated storage area.

Doses that are missed should not be made up.

On Day 1 of Cycles 1 to 4 and Cycle 6, LY2510924 should be self-administered at the clinic (time and date recorded) **after a blood sample is taken for LY2510924 PK but prior to the start of durvalumab**. Additionally, on Cycle 1 Days 2, 15, and 16, LY2510924 should be self-administered at the clinic (time and date recorded) **after a blood sample is taken for LY2510924 PK**.

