8.1.3. Other Safety Measures

8.1.3.1. Electrocardiograms

For each patient, 12-lead digital triplicate ECGs will be collected according to the Study Schedule ([Attachment 1](#)). Patients must be supine for approximately 5 to 10 minutes before ECG collection and remain supine but awake during ECG collection. Consecutive replicate ECGs will be obtained at approximately 1-minute intervals. The mean QT interval must be calculated using a corrected heart rate calculated from 1 baseline ECG using Fridericia's Correction and confirmed with the 2 additional baseline ECGs.

ECGs may be obtained at additional times, when deemed clinically necessary.

Collection of more ECGs (more replicates) than expected at a particular time point is allowed to ensure high quality records.

ECGs will be interpreted by a qualified physician (the investigator or qualified designee) at the site as soon after the time of ECG collection as possible, and ideally while the patient is still present, to determine whether the patient meets entry criteria at the relevant visit(s) and for immediate patient management, should any clinically relevant findings be identified.

If a clinically significant quantitative or qualitative change from baseline is identified after enrollment, the investigator will assess the patient for symptoms (for example, palpitations, near syncope, syncope) to determine whether the patient can continue in the study. The investigator or qualified designee is responsible for determining if any change in patient management is needed and must document his/her review of the ECG printed at the time of evaluation from at least 1 of the replicate ECGs from each time point.

All digital ECGs will be electronically transmitted to a central ECG laboratory designated by Lilly. A cardiologist at the central ECG laboratory will then conduct a full over-read on 1 of the replicates (including all intervals) and **QT/HR/RR in the other 2 replicates**. A report based on data from this over-read (confirmed ECG report) and any clinically significant findings will be issued to the investigative site. All data from the central ECG vendor's over-reads will be placed in the Lilly database for analytical and study report purposes.

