It is recognized that ECG interpretations by the investigator (or qualified designee) and by the cardiologist at the central ECG laboratory may be different. When there are differences in ECG interpretation between the investigator (or qualified designee) and the cardiologist at the central ECG laboratory, the investigator's (or qualified designee's) interpretation will be used for study entry and immediate patient management. Interpretations from the cardiologist at the central ECG laboratory will be used for data analysis and report-writing purposes.

The investigator (or qualified designee) must document his/her review of 1 of the replicate ECGs printed at the time of collection, the final over-read ECG report issued by the central ECG laboratory, and any alert reports.

QT prolongation that meets CTCAE Grade ≥ 3 criteria will be considered a DLT criterion in the Phase 1a portion of this trial; in the other parts of the study, this should be considered grounds for early withdrawal or discontinuation based on the investigator's assessment. The investigator should consider the significance of other measures of QT prolongation and may wish to consult with a cardiologist to determine whether such AEs should be reported as an SAE or should result in withdrawal of the patient from the study.

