8.2.2.1. Pharmacokinetic Samples

Bioanalytical samples collected to measure investigational product concentration will be retained for a maximum of 1 year following last patient visit for the study.

Blood samples to determine LY2510924 and durvalumab PK will be collected at times specified in [Attachment 4](#).

Blood samples will be drawn from all patients for the assessment of LY2510924 in plasma and durvalumab concentrations in serum (also known as bioanalytical samples). A maximum of 5 samples may be collected at additional time points during the study if warranted and agreed upon between both the investigator and the sponsor.

Sampling times were selected to coincide with expected C_{max} and minimum serum concentration (C_{min}) and any additional PK analysis, and with consideration to draw minimum volume of blood from patients and ensure that the patients do not need to make an extra visit to provide these samples.

Instructions for the collection and handling of bioanalytical blood samples will be provided by the sponsor. The actual date and time of LY2510924 administration must be recorded on the patient diary then reported on the CRF on the dates of interest (the most recent dose administration date and time: 1) prior to predose blood draw for PK, 2) prior to the first post-dose sample, 3) after the 24-hour sample must be recorded on eCRF). In case of additional PK collected date and time of the dose administered prior to that draw should be recorded on the eCRF.

The actual start and end date and time of durvalumab infusion administration must be recorded on the eCRF. The actual date and time that each bioanalytical blood sample was drawn must be recorded on the laboratory accession page after the sample is drawn.

LY2510924 concentrations in plasma and durvalumab concentrations in serum samples will be measured using a validated assay methodology at a laboratory designated by the sponsor.

The remaining plasma from the bioanalytical samples collected for LY2510924 PK may be pooled and used for exploratory metabolism work as deemed appropriate.

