### **6.8.7. Electrocardiograms**

Electrocardiogram (ECG) data will be summarized by visit and parameter for patients on therapy. Any abnormal ECG data will be listed by patient. Number and percentage of subjects with AEs that could be associated with abnormal ECGs will be presented, if appropriate.

If available, the number of patients meeting the following criteria with respect to QTc will be presented for maximum on-study value:

- QTc, >480 to 500 msec, and >500 msec and delta QTc >30 to 60 msec, and >60 msec.

All instances when a patient met the above criteria will be listed. Maximum absolute and change from baseline QTc data will be summarized as a continuous variable. Frequency of patients with Normal ( $\leq 480$  msec) or High ( $>480$  msec) QT/QTc interval at baseline and post baseline nominal time points will be summarized by shift table. Summaries of other ECG parameters (for example, RR, PR, and QRS) will be presented, if appropriate. A QT-concentration analysis of change from baseline in QTcF versus serum concentration may be performed, if deemed appropriate.

Lilly will review ECG data and monitor cardiac events/deaths during the course of the study.

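### No scheduled ECG follows a LY2510924 dose after repeated dosing: both later on-treatment ECGs are predose, and the only post-dose ECG follows the first dose

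*Protocol*

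**What the plan says.** Protocol Attachment 1 sets four ECG time points, all in triplicate: baseline, Cycle 1 Day 1, Cycle 1 Day 15 and Cycle 2 Day 1. The first on-treatment reading is post-dose: "Cycle 1 Day 1: ECG will be conducted 30 mins post LY2510924 dose". The other two are not: "Cycle 1 Day 15 and Cycle 2 Day 1: ECGs will be conducted predose". The row sets no later time. LY2510924 is a once-daily drug (Protocol 7.2.1.1: "LY2510924 will be self-administered SQ at rotated injection sites every day for 28 days").

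The scheduled ECGs came in with amendment (a), to "include scheduled electrocardiogram (ECG) assessments to assess QT interval length periodically during study therapy" (Protocol 5.2). Grade 3 or higher QT prolongation "will be considered a DLT criterion in the Phase 1a portion of this trial" (Protocol 8.1.3.1). Beyond the schedule, "ECGs may be obtained at additional times, when deemed clinically necessary" (same section).

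Protocol Attachment 4 draws LY2510924 PK on Cycle 1 Day 15 predose and at 0.5, 2, 4, 6 and 8 h, and on Cycle 2 Day 1 predose and at 0.5 and 4 h. SAP 6.8.7 tabulates maximum on-study QTc and change from baseline, and adds an option: "A QT-concentration analysis of change from baseline in QTcF versus serum concentration may be performed", if judged appropriate.

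**The concern.** If LY2510924 has a QT effect that follows its concentration, the effect is largest some time after a dose and after any accumulation is complete. The schedule combines these two conditions nowhere: Day 1 is post-dose without accumulation, while Day 15 and Cycle 2 Day 1 have accumulation but are at trough.

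PK is treated differently. Protocol 8.2.2.1 says "Sampling times were selected to coincide with expected" peak and minimum concentrations. On Day 1 the ECG sits beside the 0.5 h PK draw, but after repeated dosing that pairing is dropped, although the patient is in clinic for PK up to 8 h on Day 15.

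At stake are the QT component of the DLT assessment and the SAP's maximum QTc tables, which could be read as covering the highest exposure when no scheduled reading does. Protocol 5.2 notes that the 40 mg level had not been studied before.

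**Working it through.** **Step 1. What predose refers to.** On Day 15 it can only mean before LY2510924, because durvalumab is given on Day 1 of each cycle. The same sentence covers Cycle 2 Day 1. The row also asks for ECGs before associated blood draws, and the first LY2510924 draw on both days is itself predose.

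**Step 2. Count of scheduled times** (Attachments 1 and 4).

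| Visit | Prior daily doses | ECG | Same-day post-dose PK draws |
|---|---|---|---|
| Cycle 1 Day 1 | 0 | 0.5 h post-dose | 0.5, 2, 4, 6, 8 h |
| Cycle 1 Day 15 | 14 | predose | 0.5, 2, 4, 6, 8 h |
| Cycle 2 Day 1 | 28 | predose | 0.5, 4 h |

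Post-dose ECGs after repeated dosing: 0 of 2. Post-dose PK draws on those two days without a paired ECG: 5 + 2 = 7.

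**Step 3. How far the scheduled ECGs could sit from peak.** The plan gives no figure to reproduce, and no half-life, absorption rate or time of peak for LY2510924. Assumed: one compartment, first-order absorption, dosing every 24 h, half-life 6, 12, 24 or 48 h, absorption rate ka 0.5, 1 or 2 per h. With k = ln 2 / half-life, and dropping constants common to both:

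- steady state: C(t) = ka/(ka − k) × [e^(−kt)/(1 − e^(−24k)) − e^(−ka·t)/(1 − e^(−24ka))]
- first dose: C1(t) = ka/(ka − k) × [e^(−kt) − e^(−ka·t)]

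Day 15 counts as steady state in this model: after 14 doses the fraction reached is 1 − 0.5^(336/half-life), which at 48 h is 1 − 0.5^7 = 0.992.

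Example, half-life 24 h and ka = 1: k = 0.0289 and the peak falls at about 2.9 h. The bracket is 0.919/0.5 − 0.053 = 1.784 at peak and 0.5/0.5 − 0 = 1.000 at 24 h, so trough/peak = 1.000/1.784 = 56%. For the first dose at 0.5 h the bracket is 0.986 − 0.607 = 0.379, so it reaches 0.379/1.784 = 21% of steady-state peak.

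All results are percentages of steady-state peak, ranged over ka:

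| Half-life | Trough | Day 1, 0.5 h | Steady state, 0.5 h | Steady state, 2 h | Steady state, 4 h |
|---|---|---|---|---|---|
| 6 h | 8–12 | 31–68 | 42–75 | 89–99 | 79–100 |
| 12 h | 28–36 | 21–51 | 56–79 | 89–100 | 90–100 |
| 24 h | 53–61 | 12–33 | 72–86 | 92–100 | 95–100 |
| 48 h | 73–78 | 7–19 | 84–92 | 95–100 | 98–100 |

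Modelled time of peak is about 1.5 to 4.8 h.

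**Step 4. Illustration only.** If QT effect were proportional to concentration, a hypothetical 20 msec effect at peak would show at trough as 20 × the trough fraction: about 1.6–2.5 msec at a 6 h half-life, 5.7–7.2 at 12 h, 10.7–12.1 at 24 h and 14.6–15.6 at 48 h.

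**The case against.** The plan has several answers. Investigators may take extra ECGs, and Protocol 8.4 lets the sponsor modify collection times in the light of safety and PK data. QT is not a named objective, and this is not a dedicated QT study. Patients with QTc of 450 ms or more, a QT history or QT-prolonging drugs are excluded; triplicates are over-read centrally; and there are discontinuation rules for QT. Trough ECGs also have their own use, since they can show a delayed or accumulating effect. With a long half-life, trough is already near peak.

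Much of this stands, and it rules out two stronger readings. A reader might infer that QT at post-dose repeated exposure will never be measured. The documents do not support that: discretionary ECGs are allowed, so the gap is one of schedule. A reader might also infer that a committed QT-concentration analysis is left without data. That analysis is optional, and it would still have one post-dose pair on Day 1 and two trough pairs, across the dose levels tested.

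What does not stand is that these provisions close the gap. Discretionary ECGs depend on an event or a judgement and have no set time after dosing, and the exclusions and the over-read do not supply a post-dose reading.

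**Conclusion.** The point holds as a gap in the schedule. No scheduled ECG captures post-dose LY2510924 exposure after repeated dosing: 0 of 2 readings, against 7 post-dose PK draws on the same two days. That count rests on the documents alone.

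The size rests on the assumed model. Trough is about 8% to 78% of steady-state peak, and the Day 1 reading about 7% to 68%. Neither reaches peak anywhere in the range, but at a 48 h half-life the trough shortfall is only about a quarter. Treating the drug as if it peaked at the moment of injection, with trough = 0.5^(24/half-life), would give 6%, 25% and 50% at 6, 12 and 24 h. That overstates the gap, because a subcutaneous dose peaks later. The documents do not show that LY2510924 prolongs QT, so this is an inexpensive improvement to what the ECGs can detect and not evidence of a missed effect.

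**What to change.** In the Attachment 1 ECG row, re-time the existing Cycle 1 Day 15 triplicate ECG to just before the post-dose LY2510924 PK draw nearest the time of peak known to the sponsor. In the assumed model that is the 2 h draw (89% to 100% of peak) or the 4 h draw (79% to 100%). Copying Day 1's 30 minutes would reach only 42% to 92%. Keep Cycle 2 Day 1 predose as the trough reading. If the sponsor prefers the present times, the protocol should state why trough ECGs are enough.

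If the optional analysis in SAP 6.8.7 is run, name LY2510924 and pair QTcF with its plasma concentration. The SAP sentence says serum and names no drug, whereas Protocol 8.2.2.1 measures LY2510924 in plasma and durvalumab in serum.

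Cost: no new visit and no new procedure, since the patient is already in clinic for the Day 15 PK draws. One of the two repeat-dose trough ECGs is given up.
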